3.4.4 Analysis Visits

In addition to study visits described above, analysis visits based on dosing cycle of each dose level will be derived for descriptive summary during the main treatment period as follows:

- 1st Cycle of Exposure: Day 1, Day 8, Day 15 and Day 22
- 2nd Cycle of Exposure: Day 1, Day 8, Day 15 and Day 22
- 3rd Cycle of Exposure: Day 1, Day 8, Day 15 and Day 22
- 4th Cycle of Exposure: Day 1, Day 8, Day 15 and Day 22
- 5th Cycle of Exposure: Day 1, Day 8, Day 15 and Day 22
- 6th Cycle of Exposure: Day 1, Day 8, Day 15 and Day 22
- Xth Cycle of Exposure: Day 1, Day 8, Day 15 and Day 22 for patients who had treatment cycle(s) beyond Cycle 6
- Last value on-treatment (Last post-baseline visit during the main on-treatment period including unscheduled visits within each dose level)

For example, if a patient received 200 mg QD at Cycle 1, 400 mg QD at Cycle 2 and Cycle 3 and 300 mg BID at Cycle 4 and Cycle 5, the scheduled visits will be mapped to the analysis visits as follows:

Dose Level	Scheduled Visit	Analysis Visit
200 mg QD	Cycle 1 – Day 1, 8, 15 and 22	200 mg QD: 1st Cycle of Exposure – Day 1, 8, 15 and 22
400 mg QD	Cycle 2 – Day 1, 8, 15 and 22	400 mg QD: 1st Cycle of Exposure – Day 1, 8, 15 and 22
400 mg QD	Cycle 3 – Day 1, 8, 15 and 22	400 mg QD: 2 nd Cycle of Exposure – Day 1, 8, 15 and 22
300 mg BID	Cycle 4 – Day 1, 8, 15 and 22	300 mg BID: 1 st Cycle of Exposure – Day 1, 8, 15 and 22
300 mg BID	Cycle 5 – Day 1, 8, 15 and 22	300 mg BID: 2 nd Cycle of Exposure – Day 1, 8, 15 and 22

Note: Visits occurred at and after the visit where dose reduction occurred will not be mapped.

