- 7. T/B/NK/monocyte counts (i.e., CD3, CD4, CD8, CD14, CD19, CD16/56), and B cell subsets (i.e., naïve, memory and plasmablasts)
- 10. On Day 1 of each new dose level cycle, patients will take their dose in the clinic and remain in the clinic for intensive PK sampling for 6 hours following the first dose at time points: 0, 0.5, 1, 1.5, 2 (time windows for first 2 hours are ± 2 minutes), 3, 4, and 6 hr (time windows for > 2 hr samples are ±5 minutes). On subsequent clinic visits of each dosing cycle, patient should take their dose in the morning before the clinic visit (whether dosing is QD or BID), and the PK sample is taken at random times after last dose (with time of last dose recorded on CRF, no time window).
- 11. If still taking rilzabrutinib (PRN1008)
- 12. ITP-BAT scale performed at all clinic visits but not laboratory-only visits
- 13. Assessments on Day 1 of each 28-day treatment Cycle are performed pre-dose; ECGs and PK samples are also collected at additional times post-dose per Footnote 4 (ECGs) and Footnote 10 (PK samples).
- 14. Weekly lab visits between the in clinic visits occur each cycle at Day 22 (CXD22) and weekly between Day 85 and Day 169 on Days 92, 99, 106, 120, 127, 134, 148, 155 and 162. The lab visits have a visit window of ± 3 days.

Page 17 of 57

Table 4 Schedule of Assessments (protocol version 8.0 to version 14.0)

			On-treatment cl		Early			
	Screening (D-28 to D-1)	C1D1 only	CXD1 (first day of each cycle) ¹³	CXD15	D169 (last day of active rilzabrutinib (PRN1008) treatment)	End of Study D197	Weekly lab visit between clinic visits ¹⁴	Withdrawal/ Unscheduled visit
Clinic visits ¹	Х		Х	Х	Х	Х		Х
Laboratory Only Visits for Hematology, differential & retics							Х	
Informed Consent	Х							
Inclusion/Exclusion Criteria	Х	X ¹						
AEs	Х	Х	Х	Х	Х	Х		Х
Concomitant Medications	Х		Х	Х	Х	Х		Х
Dose-escalation points ²			Х					
Height	Х							
Weight	Х		Х		Х	Х		Х
Physical exam/med history ³	Х		Х	Х	Х	Х		Х
Online cognitive testing ¹⁸	X ¹⁵		Х		Х	Х		Х
ECG (12-lead, single)	Х							X ³
ECG (12-lead, triplicate) ⁴			Х			X ¹⁷		
Vital Signs	Х		Х	Х	Х	Х		Х
Urinalysis	Х		Х	Х	Х	Х		Х
Hep B &C, HIV	Х							
Pregnancy test⁵	Х		Х		Х	Х		Х
FSH ⁶	Х							
ABO and Rh Blood Type	Х							
Serum Chem	Х		Х		Х	Х		Х
Hematology, differential, retics.	Х		Х	Х	Х	Х		Х
T/B/NK/monocyte counts ⁷			Х		Х	Х		
PT/INR PTT	Х		Х		Х	Х		
Mean platelet volume			Х					
Immature platelet fraction			Х					

Principia Biopharma Page 18 of 57

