			On-treatment clinic visits, treatment cycles of 28days, X≤6 ¹⁶					Early
	Screening (D-28 to D-1)	C1D1 only	CXD1 (first day of each cycle) ¹³	CXD15	D169 (last day of active rilzabrutinib (PRN1008) treatment)	End of Study D197	Weekly lab visit between clinic visits ¹⁴	Withdrawal/ Unscheduled visit
	,	,	,,,,,		,			
ITP-BAT Bleeding Scale ¹²	Х		X	Х	X	Х		X

- 1. Clinic/laboratory visit windows are ± 3 days for all dosing period and lab visits. Labs to confirm eligibility prior to Cycle 1 Day 1 may be taken up to 3 days in advance of Cycle 1 Day 1.
- 2. See protocol section 4.3 of the protocol dose-escalation rules
- 3. Full physical examination at screening, abbreviated physical examination at other visits.
- 4. Triplicate ECG pre-dose and at 2 hours post-dose (± 15 minutes) on the first day of dosing at each new dose level. Where patients are continuing into a new cycle at the prior dose level, ECG is not required.
- 5. For women of childbearing potential only. Serum pregnancy tests are performed at screening, urine pregnancy tests are performed at other visits.
- 6. To confirm postmenopausal status for women who are not surgically sterile and of reproductive potential
- 7. T/B/NK/monocyte counts (i.e., CD3, CD4, CD8, CD14, CD19, CD16/56), and B cell subsets (i.e., naïve, memory and plasmablasts)
- 10. On Day 1 of each new dose level cycle, patients will take their dose in the clinic and remain in the clinic for intensive PK sampling for 6 hours following the first dose at time points: 0, 0.5, 1, 1.5, 2 (time windows for first 2 hours are ± 2 minutes), 3, 4, and 6 hr (time windows for > 2 hr samples are ±5 minutes). On subsequent clinic visits of each dosing cycle, patient should take their dose in the morning before the clinic visit (whether dosing is QD or BID), and the PK sample is taken at random times after last dose (with time of last dose recorded on CRF, no time window). Where patients are continuing into a new cycle at the prior dose level, PK sampling is not required.
- 11. If still taking rilzabrutinib (PRN1008)
- 12. ITP-BAT scale performed at all clinic visits but not laboratory-only visits
- 13. Assessments on Day 1 of each 28-day treatment Cycle are performed pre-dose; ECGs and PK samples are also collected at additional times post-dose per Footnote 4 (ECGs) and Footnote 10 (PK samples).

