3.3 Treatment Groups

3.3.1 Treatment Group Labels

The following treatment group labels will be used in the tables, listings and figures:

Treatment Group Label	Patients Included
Overall	All patients in the population will be included in this group.
Starting Dose 200 mg QD	Patients will be classified to these groups according to the starting
Starting Dose 400 mg QD	dose received. Each patient will be assigned to only one of these
Starting Dose 300 mg BID	groups.
Starting Dose 400 mg BID	
200 mg QD	Patients are evaluable in the dose group(s) if the dose level was
400 mg QD	received during the defined period (Sections 3.4.1and 3.5.2). Since
300 mg BID	most patients received more than one dose, a given patient can be
400 mg BID	assigned to multiple dose levels.
	For each of the following type of analyses, patients will be classified to
	each dose level based on:

Treatment Group Label	Patients Included
	 Dose level received prior to the visit for responder analyses, time-to analyses and analyses of proportion of patients meeting an endpoint, i.e., percent of weeks with platelet counts ≥ 50,000/μL. Dose level received at the onset of event for adverse events, and bleeding events analyses. Adverse events started after date of last dose of study drug will be attributed to the last dose level received. Dose level received during the time the medication was taken for any medication analyses. Medications taken after date of last dose of study drug will be attributed to the last dose level received.

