5.4.3 Exploratory Efficacy Endpoints

5.5 Safety Analyses

The Safety Population will be used for the safety analyses. The summary statistics for the main period will be done by starting dose and overall for all study visits and by cycle of exposure (as appropriate), unless specified otherwise. Descriptive summary will be generated for data collected during the LTE period as needed.

Patient data listings will be listed by starting dose, patient, dose level and study visit or start date of event if applicable, indicating on-treatment period or LTE on-treatment period.

In addition to standard analyses of all adverse events, dose limiting toxicities, laboratory tests, ECG data, and vital signs, the analyses of safety will include the following endpoints:

- 1) Percentage of participants receiving rescue medication at each dosing level and overall
- 2) Proportion of patients with an Intensity Grade 2 or higher bleeding event at each dosing level and overall
- 3) Bleeding scale (ITP Bleeding Assessment Tool [ITP-BAT]) at the end of treatment period for each dosing level and overall

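### Part A by-cycle summaries (SAP 3.4.4) place pre-dose values from the day of escalation under the new dose, although they reflect the dose just completed; chemistry and coagulation are most affected

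*SAP*

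**What the plan says.** Section 3.4.4 of the Part A SAP creates a second set of visits: "analysis visits based on dosing cycle of each dose level will be derived for descriptive summary during the main treatment period". Its example patient takes 200 mg QD in Cycle 1, 400 mg QD in Cycles 2 and 3, and 300 mg BID in Cycles 4 and 5. Cycle 2 is mapped to "400 mg QD: 1st Cycle of Exposure – Day 1, 8, 15 and 22", and Cycle 4 is treated the same way under 300 mg BID. A last on-treatment value is also derived for each dose level, defined as "Last post-baseline visit during the main on-treatment period including unscheduled visits within each dose level".

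Footnote 13 to Tables 3 and 4 (SAP 2.7) fixes the timing: "Assessments on Day 1 of each 28-day treatment Cycle are performed pre-dose". Only ECG and PK have additional post-dose samples that day.

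Table 4 (versions 8.0 to 14.0) schedules serum chemistry and PT/INR/PTT within a cycle on Day 1 only. The visits between clinic visits are "Laboratory Only Visits for Hematology, differential & retics", so platelets are measured weekly but chemistry and coagulation are not. Under version 7.0 (Table 3), chemistry and coagulation were also drawn on Day 8.

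Safety summaries for the main period are presented "by starting dose and overall for all study visits and by cycle of exposure (as appropriate), unless specified otherwise" (SAP 5.5); section 5.4 says the same for efficacy. For other outputs, section 3.3.1 classifies patients by "Dose level received prior to the visit for responder analyses, time-to analyses and analyses of proportion of patients meeting an endpoint".

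**The concern.** A sample taken before the first dose of a new level carries no effect of that level. It is the end-of-cycle measurement for the level the patient has just finished, after about 28 days on it. Filing it under the new level moves the measurement up one dose. For a test drawn several times per cycle this dilutes the by-dose picture. For a test drawn only on Day 1, it can be the whole picture for a level held for one cycle.

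Part A is the dose-finding part. Protocol 10.10 plans safety summaries by dose level within that level's time boundaries, and protocol 10.10.2 foresees exploring dose level against laboratory changes if any are seen. In the by-cycle display, a liver-enzyme change arising on one dose would appear under the next. A starting dose held for one cycle would have no scheduled post-baseline chemistry and could look clean for that reason alone.

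**Working it through.** The plan states no figure for this, so the check counts visits.

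**Check of the attribution rule.** Section 5.4.1 attributes a response to the dose at the visit before. Applied to its Example 1, this gives 200, 200, 200, 400, 400, 400, 600, 600 for C1D8 to C3D15, which matches the printed column. There C2D1 belongs to 200, although 400 is dispensed that day.

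**Inputs.**
- Dose paths: the 3.4.4 example; cohort 1 escalating every cycle, from SAP Tables 1 and 2; and the same path extended so that 400 mg BID is held for 24 weeks, i.e. six 28-day cycles (protocol 4.1), giving 3 + 6 = 9 cycles.
- Draws per cycle, k: 1 for chemistry and coagulation from version 8.0; 2 under version 7.0 (Days 1 and 8); 4 for platelets (Days 1, 8, 15, 22).
- C1D1 is excluded because it is baseline. The last-day-of-treatment, end-of-study, early-withdrawal and unscheduled visits are not counted.

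**Formulas.** With c cycles, scheduled post-baseline values = k × c − 1. Each escalation contributes one pre-dose Day 1 value, so misplaced values = number of escalations.

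**The SAP's own example, chemistry and coagulation from version 8.0.**

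| Draw | Label under 3.4.4 | Dose actually reflected |
|---|---|---|
| C1D1 | 200 mg QD | none (baseline) |
| C2D1 | 400 mg QD | 200 mg QD |
| C3D1 | 400 mg QD | 400 mg QD |
| C4D1 | 300 mg BID | 400 mg QD |
| C5D1 | 300 mg BID | 300 mg BID |

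Two of the 4 post-baseline values are misplaced. Counts for 200 mg QD, 400 mg QD and 300 mg BID are 0, 2, 2 as mapped, and 1, 2, 1 by the dose taken before the draw.

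**All paths.**

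| Path | Escalations | Chemistry/coagulation | Platelets |
|---|---|---|---|
| SAP example, 5 cycles | 2 | 2/(5 − 1) = 2/4 = 50% | 2/(20 − 1) = 2/19 = 10.5% |
| Cohort 1, 6 cycles | 3 | 3/(6 − 1) = 3/5 = 60% | 3/(24 − 1) = 3/23 = 13.0% |
| Cohort 1, 9 cycles | 3 | 3/(9 − 1) = 3/8 = 37.5% | 3/(36 − 1) = 3/35 = 8.6% |
| Cohort 1, version 7.0, 3 cycles | 2 | 2/(6 − 1) = 2/5 = 40% | 2/(12 − 1) = 2/11 = 18.2% |

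**One-cycle levels.** In both later-version cohort 1 paths, 400 mg QD and 300 mg BID each hold one scheduled chemistry or coagulation value, and it is the pre-dose one (1 of 1). It falls after baseline, so it meets the definition of the last on-treatment value for that level unless an unscheduled sample was taken.

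**After reassignment.** Moving escalation-day values to the preceding dose brings the misplaced count to 0 in every path.

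**The case against.** The strongest reply is that 3.4.4 covers descriptive summaries only and that its row is labelled Day 1. Read with footnote 13, a careful reader could take that row as a pre-dose entry value. This has some force for the by-visit row. It has none for the within-level last value, which carries no Day 1 label, and nothing in the SAP marks the value as a reference or excludes it.

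Second, the by-cycle display is one of several and is used only where appropriate. Starting-dose and overall tables keep C2D1 at its study visit, so the absence of post-baseline chemistry for a one-cycle starting dose arises only inside the by-cycle display. This stands, and it limits the reach of the point. The laboratory text does not, however, exempt itself from that display.

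Several stronger readings are tempting, but the documents do not support them:

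- *The primary result or the dose choice is biased.* Responder, time-to and proportion analyses use the dose received before the visit (3.3.1, 5.4.1). Starting-dose decisions rested on review of DLTs and sustained platelet responses (protocol 11.1), and no hypothesis is tested (SAP 3.8).
- *The SAP contradicts itself.* Sections 3.3.1 and 3.4.4 govern different outputs. The same C2D1 platelet count can sit under 200 mg for response and under 400 mg in a by-cycle table. That is an inconsistency of approach, not two rules for one output.
- *Every chemistry draw is mislabelled in a patient escalating each cycle.* That would count C1D1, which is baseline, and would ignore later cycles at 400 mg BID, which are labelled correctly.
- *TPO is misreported.* The protocol's Appendix 3 schedules TPO within a cycle on Day 1 only, but the SAP's exploratory analysis text is not visible, so its use of 3.4.4 for TPO cannot be confirmed.
- *Shift, maximum/minimum and liver-threshold tables are wrong by dose.* Section 5.5.6 does not say that these are produced by current dose level.

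**Conclusion.** The point holds for the Part A cycle-of-exposure summaries. As written, the rule gives the wrong dose label to every pre-dose assessment made on an escalation day. For chemistry and coagulation from version 8.0, this affects 37.5% to 60% of scheduled post-baseline values in the paths examined, and all of them for an intermediate level held for one cycle. For weekly platelets it is 8.6% to 13.0% in the same paths, and 18.2% in the short version 7.0 path.

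These are shares within a single patient's dose path, not trial-wide rates; the documents do not say how many patients escalated, or when. They assume that Day 1 samples were drawn pre-dose as scheduled and that no unscheduled samples fill the gaps. A Day 1 that continues the same dose is labelled correctly, and visits from a dose reduction onward are not mapped. The secondary endpoint on average post-Day 1 platelet change (5.4.2.3) is left out of the count, because its text does not say whether Day 1 means study Day 1 or Day 1 of the level.

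The repair is worth making because these tables describe laboratory safety by dose. No primary or responder result depends on it.

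**What to change.** In 3.4.4, assign each assessment taken before the first dose of a new level to the preceding level as its end-of-cycle value. Include it in that level's last on-treatment value and in any other post-baseline summary produced by dose level. Under the new level, show it only, if at all, as a labelled pre-dose reference, excluded from that level's last-value and post-baseline statistics. Post-dose ECG and PK samples stay under the new level. This carries the prior-dose principle of 3.3.1 into the descriptive tables.

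The cost is one SAP rule, a re-derivation of the ADaM analysis visits and a re-run of the by-cycle tables, with no new data. The Part B SAP (section 1.1) notes that a Part A study report has already been prepared, so the re-run tables would most naturally go into an addendum.

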3.4.5 Baseline for Platelet Count

The average of the 2 screening results and the Cycle 1 Day 1 result will be used as the Baseline value for platelet count. If at least one of the platelet counts is missing, the average of the non-missing platelet counts will be used. This baseline value will be used for the main treatment period and LTE period analyses.

3.4.6 Baseline for Lab and Vital Signs

If measurement date and time are available, the last value measured prior to the date and time of first rilzabrutinib treatment will be used as the Baseline value for labs and vital signs.

If only the measurement date is available but time is not available, the value measured at Cycle 1 Day 1 will be used as the Baseline value. If Cycle 1 Day 1 result is missing and the screening result is available,

then the screening result will be used as Baseline. This baseline value will be used for the main treatment period and LTE period analyses.

3.4.7 Baseline for ECG

The average of the non-missing triplicate ECG results measured at Cycle 1 Day 1 will be used as the Baseline value for the numerical ECG parameters. If all 3 results at Cycle 1 Day 1 are missing, the single value measured at Screening will be used as Baseline.

For the categorical result of overall ECG assessment, the worst finding of the triplicate assessments collected at Cycle 1 Day 1 will be used as the Baseline result. If all 3 results are missing, the overall ECG assessment collected at Screening will be used as Baseline.

3.4.8 Pre-treatment vs. treatment emergent adverse events

Pre-treatment events are the events that started prior to the first study drug dosing.

Treatment emergent adverse events (TEAEs) are the events started on or after the first study drug dosing. The CRF variable "Did this AE occur before the first dose?" will be used if the start date of the event is the same as the date of first study drug dosing.

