### 10.10.1 Adverse Events

The original verbatim AE terms recorded on the patient's case report form (CRF) by the Investigator will be standardized by assigning preferred terms and system organ classes from the most recent available version of the Medical Dictionary for Drug Regulatory Affairs (MedDRA).

Adverse events will be codified using the NCI CTCAE v5.0, which provides a mechanism for grading the severity of the AE.

Treatment emergent adverse events include all AEs that start on or after the first dose of study medication, or AEs that are present prior to the first dose of study medication, but worsen after the first dose of study medication up to and including the final study medication dosing date. Adverse events that occur after the first dose of study medication or worsen after the first dose of study medication are treatment-emergent adverse events (TEAEs). Adverse events that occur prior to the first dose of study medication are pre-treatment adverse events (ie, non-TEAEs). The number and percent of patients with any TEAEs will be displayed by system organ class and preferred term by dosing level and overall. Within each preferred term, patients will be counted only once if they had more than one event reported during the dosing period. The same summary will be performed for all serious TEAEs and all TEAEs causing discontinuation of study drug.

Treatment-emergent adverse events will also be summarized by greatest reported severity grade (Grades 1–5) for each event/preferred term. Counts will indicate patients reporting one or more TEAEs that map to the severity grade classification for each preferred term. At each level of summarization (system organ class or event preferred term) patients are only counted once. TEAEs will be summarized by greatest reported relationship in a similar manner. A listing will be produced for all patients who reported serious TEAEs or who discontinued study medication due to TEAEs.

All TEAEs will be listed individually by patient. In addition, a separate listing will be produced for AEs that are not treatment-emergent.

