# 10.12 Statistical Analysis Plan

A detailed SAP will be developed and finalized before the study database is locked, which will supersede the statistical analysis methods described in the protocol.

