Section 2.3, Overall benefit-risk assessment, Safety profile	Revised text to state: "Importantly, there were no related thrombin or major bleeding events in the clinical experience with PRN1008 up to date."	Updated clinically relevant safety information.
Section 2.3, Overall benefit-risk assessment, Efficacy	Added text from preliminary review of the efficacy data in Part A.	
Section 4.1, Overall study design and plan Part A, Long term extension; Section 4.2, Overall study design and plan Part B	Updated criteria to better define the population that may receive clinical benefit of the study drug. Delete text to reflect the completion of the dose escalation part of the study. Addition of Part B overall study design and plan.	Clarification, updates related to completion of the dose-escalation part of the study, addition of Part B to the study.

Description of Change	Brief Rationale
Added text for Part B	Addition of the maximum number of participants in Part B.
Added text for Part B.	Addition of Part B study duration and duration of patient participation.
Added permitted concomitant medications for Part B.	Inclusion of Part B of the study.
Added "Part A" before existing text. Added text for Part B.	Addition of Part B PK sampling information.
This section was deleted.	There will no longer be an analysis of the screening population as it is the same as the ITT population.
This section was deleted.	Requirement for reconsenting removed.
Added text for Part B statistical analysis.	Inclusion of Part B of the study.
Text revised.	Clarification.
Updated text to define the reported AEs that start before the first dose of study drug as pre-treatment events and those events that start after the first dose of study drug or worsen after the first dose of study drug as TEAEs.	Clarification.
Added text for Part B.	Inclusion of Part B of the study.
Text revised.	Addition of Part B changes regarding only 1 dose to be used in Part B.
Revised text to clarify that the history of rescue medication collection in Part A was not limited to 12 weeks and that Part B will assess only 1 dose of PRN1008.	Clarification; inclusion of Part B of the study.

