1 INTRODUCTION

The purpose of this document is to describe the final statistical analysis for Part A of the PRN1008-010 study. This statistical analysis plan (SAP) is a based on the protocol version 14.0 dated 12 Aug 2020 and case report form dated 23 SEP 2019.

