4.7.2 Adverse events

General common rules for adverse events

All AEs will be graded according to National Cancer Institute Common Terminology for Adverse Events (NCI-CTCAE) version v5.0, and coded to a lower-level term (LLT), preferred term (PT), high-level term (HLT), high-level group term (HLGT), and associated primary system organ class (SOC) using the Medical Dictionary for Regulatory Activities (MedDRA) currently in effect at Sanofi at the time of the database lock.

The AEs will be analyzed in the following 2 categories:

- Pre-treatment AEs: AEs that developed, worsened, or became serious during the pre-treatment period.
- Treatment-emergent adverse events (TEAE)s: AEs that developed, worsened or became serious during the treatment-emergent period (including the on-treatment and post-treatment periods defined in Section 4.1).

The primary focus of AE reporting will be on TEAEs. Pre-treatment and post-treatment AEs will be flagged in the AE listing.

An AE with incomplete or missing date/time of onset (occurrence, worsening, or becoming serious) will be classified as a TEAE unless there is definitive information to determine it is a pre-treatment AE.

If the assessment of the relationship to IMP is missing for an AE, this AE will be assumed as related to IMP. If the CTCAE grade is missing for 1 of the treatment-emergent occurrences of an AE, the grade will be imputed with the maximal grade of the other occurrences. If the grade is missing for all the occurrences, the grade will be left as missing.

Multiple occurrences of the same event in the same participant will be counted only once in the tables within a treatment phase, using the maximum (worst) grade by treatment phase. Summaries will be provided for all grades combined and for grade ≥ 3 (including grade 5). Missing grades, if any, will be included in the "all grades" category.

The AE tables will be sorted as indicated in Table 4.

Table 4 - Sorting of AE tables

AE presentation	Sorting rules
SOC, HLGT, HLT and PT	By the internationally agreed SOC order and by alphabetic order of HLGTs, HLTs and PTs
SOC and PT	By the internationally agreed SOC order and decreasing frequency of PTs ^a
PT	By decreasing frequency of PTs

a The table of all TEAEs presented by SOC and PT will define the presentation order for all other tables (e.g., treatment-emergent SAE) presented by SOC and PT, unless otherwise specified.

Property of the Sanofi group - strictly confidential

Page 21

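### The Part A SAP defines treatment-emergent events by start date only and omits, without declaring it, the protocol's rule for events that worsen on drug, so Part A TEAE rates could be understated

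*SAP*

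**What the plan says.** **Part A SAP, 3.4.8.** The rule has two halves: "Treatment emergent adverse events (TEAEs) are the events started on or after the first study drug dosing", and "Pre-treatment events are the events that started prior to the first study drug dosing". A CRF question settles events dated on the day of first dose, and it too asks only about onset. Neither half looks at what happens to an event later.

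**Protocol, 10.10.1.** Besides events with onset on or after first dose, it counts "AEs that are present prior to the first dose of study medication, but worsen after the first dose of study medication". A second sentence repeats the worsening rule. A third classes events that occur before first dose as non-TEAEs.

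**Part B SAP, 4.7.2.** TEAEs are "AEs that developed, worsened or became serious during the treatment-emergent period".

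**Timing and precedence.** The protocol's amendment history (Appendix 10, version 13, 5 March 2020) records that the text was changed to define "those events that start after the first dose of study drug or worsen after the first dose of study drug as TEAEs". The Part A SAP "is a based on the protocol version 14.0 dated 12 Aug 2020", so the worsening rule was already in the protocol it was written from. Protocol 10.12 describes the SAP as a document "which will supersede the statistical analysis methods described in the protocol". Part A SAP 4.5 lists changes from the protocol. Its visible rows cover analysis populations, secondary and exploratory endpoints, added efficacy analyses and reclassified safety endpoints, but not the TEAE definition.

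**The concern.** The TEAE flag feeds nearly every adverse event table in Part A SAP 5.5.1, including those by intensity, relationship, seriousness and discontinuation. Bleeding events under 5.5.4 are also picked from the preferred terms of TEAEs. Safety is the first objective listed for Part A.

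Event collection begins at screening, up to 28 days before Day 1 (protocol 11.2 and the synopsis), so some events can be ongoing at first dose. If one of these worsens on drug and stays a single record, 3.4.8 keeps it pre-treatment. It then appears only in the pre-treatment table, which 5.5.1 produces for the overall group with no dose level, and in the listings. A Grade 2 event from screening that reached Grade 3 on treatment would be missing from the Grade 3 or higher table.

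Parts A and B also feed a common long-term extension, and their TEAE tables would rest on different definitions.

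**Working it through.** The plan states no adverse event rate, and the Part A SAP plans no hypothesis tests, so there is no figure to reproduce. The check sets the three definitions side by side and then shows a scale.

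**Step 1. Classify each type of event under each definition.**

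| Course of the event | Part A SAP 3.4.8 | Protocol 10.10.1 | Part B SAP 4.7.2 |
|---|---|---|---|
| Starts on or after first dose | TEAE | TEAE | TEAE |
| Starts in screening, does not change | Pre-treatment | Not a TEAE | Not a TEAE |
| Starts in screening, worsens on drug, entered as a new record dated at worsening | TEAE | TEAE | TEAE |
| Starts in screening, worsens on drug, kept as one record | **Pre-treatment** | **TEAE** | **TEAE** |
| Starts in screening, becomes serious on drug without otherwise worsening, kept as one record | Pre-treatment | Not named | TEAE |

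The Part A SAP and the protocol differ only in the fourth row. The Part A SAP also differs from the Part B SAP in the fifth.

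**Step 2. Look for a rule elsewhere in the Part A SAP that restores the fourth row.** The partial-date rules (3.5.1) impute missing onset dates. The analysis rules (5.5.1) assign TEAEs to dose levels by start date. Neither mentions worsening.

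**Step 3. Direction.** For a given set of records and imputed dates, the Part A set of TEAEs is the protocol's set or a subset of it. The omission can remove events from the tables but cannot add any.

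**Step 4. Scale.** If *k* patients fall in the fourth row and have no other event in the table row concerned, the incidence changes by 100 × *k*/*N* percentage points. The documents do not give *k*; 0 to 3 is an assumption. *N* = 60 is the approximate Part A enrolment (SAP 2.3). *N* = 6 is the upper sentinel cohort size, used here as an example of a small denominator.

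| *k* | *N* = 60 | *N* = 6 |
|---|---|---|
| 0 | 0.0 | 0.0 |
| 1 | 1/60 = 1.7 | 1/6 = 16.7 |
| 2 | 2/60 = 3.3 | 2/6 = 33.3 |
| 3 | 3/60 = 5.0 | 3/6 = 50.0 |

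These are ceilings for each *k*: a patient who already has another event in the row adds nothing to it.

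**The case against.** The tempting stronger reading is that Part A safety rates *are* understated. The documents do not support that. Protocol 11.3 has pre-existing conditions that worsen during the study reported as adverse events. If sites enter each worsening as a new record with its own onset date, the start-date rule already counts it and nothing is lost. No document says whether a screening event already on the CRF is split in this way or has its grade changed on the same record. The effect may therefore be zero.

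Other points on that side:

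- **The protocol is not uniform.** The synopsis and sections 3.3.1 and 10.1 tie treatment emergence to receipt of the first dose without mentioning worsening, and one sentence of 10.10.1, read alone, matches the Part A SAP. This stands as a remark on loose drafting. But 10.10.1 is the detailed definition and states the worsening rule twice.
- **The SAP may supersede the protocol.** It may, but 4.5 exists to declare such changes and does not declare this one.
- **Incomplete onset dates lean towards TEAE.** A wholly missing date, or a partial date in the month or year of first dose, leads to classification as treatment-emergent. That can raise counts, but it does not reach an event with a complete pre-dose date.
- **Worsening can be seen elsewhere.** The listings of adverse events and serious adverse events are not restricted to TEAEs, and shift tables cover the bleeding scale, laboratory values, vital signs, ECG and physical examination. Protocol 11.3 also limits the recording of typical ITP signs, so the effect on bleeding tables may be small. This lowers the stakes, but the TEAE summaries would still be incomplete.
- **Parts A and B differ in other ways.** They use broad and narrow haemorrhage searches and different MedDRA versions. One shared definition would not make the tables fully comparable, but it would remove one avoidable difference.

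**Conclusion.** The discrepancy is established from the text. Part A SAP 3.4.8 leaves out the worsening part of the protocol's definition, the Part B SAP keeps it, and 4.5 does not declare the change. Part A TEAE, Grade 3 or higher, serious, and Grade 2 or higher bleeding rates could therefore be understated, and they are not on the same definition as Part B.

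The size cannot be derived from the documents. It depends on how many events were ongoing at first dose, how many of those worsened, and whether each worsening became a new record. It is zero if every worsening was entered as a new record. Otherwise it is at most 1.7 percentage points per affected patient at *N* = 60, and more in a small dose group. The omission itself can only lower the counts relative to the protocol definition. It is worth correcting because the rule as written gives the wrong classification in an identifiable case and the repair is cheap.

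**What to change.** 1. **Definition.** In 3.4.8, adopt the protocol 10.10.1 definition: an event is treatment-emergent if it starts on or after first dose, or if it was present before first dose and worsens after it.
2. **Window.** Reconcile the end of the window. One sentence of 10.10.1 closes it at the last dosing date, while protocol 10.1 expects TEAEs in post-treatment follow-up, and Part A SAP 3.4.2 includes follow-up in the main period for patients who did not enter the extension.
3. **Dose level.** Section 5.5.1 assigns events by start date, which gives no dose level to an event that began before dosing. Assign a worsened event to the dose level on the recorded date of worsening, or on the new record's onset date where worsening is captured that way. No document shows that a worsening date is collected, so check this first. If neither date exists, the assignment cannot be derived, and 4.5 should say so.
4. **Becoming serious.** If this is added to match Part B, label it as an extension, because protocol 10.10.1 does not contain it.
5. **Declaration.** List any remaining departure in 4.5. If worsening was always entered as a new record, state that in 3.4.8.
6. **Count.** Report how many events ongoing at first dose later worsened. The Part B SAP (1.1) says the Part A report has already been prepared, so this could be an addendum, with the TEAE tables re-run if the count is not zero.

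The cost is a short text change and one derivation change, provided the dates exist. The reported rates may become slightly less favourable.
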